## **7.6 Treatment Compliance**

Administration of IP will be conducted by study staff **or subject (refer to [Table 7-1](#))** on scheduled visits. Subjects enrolled by the DCTS will be permitted to self-inject the IP in PFS at their own physical location (eg, home) under observation from the investigator/member of the study team via videoconference, after being trained on day 1 by the qualified study personnel on self-injections. Each injection will be documented.

Noncompliance is to be documented in the medical file/source documentation and will be reflected in the electronic CRF. Noncompliant subjects are to be re-educated on the importance of adhering to the IP administration schedule and reminded that repeated cycles of noncompliance could be a reason for discontinuation of study treatment.

## **7.7 Treatment of Overdose**

Overdose with this product has not been reported. No specific antidote exists. In the case of an overdose, the subject should be treated symptomatically, and supportive measures implemented as necessary.

## **7.8 Prior and Concomitant Treatment**

### **7.8.1 Prior Treatment**

For prior migraine preventive medications, ending 2 months prior to start of baseline, therapy name, indication, dose, unit, frequency, start and stop dates will be collected in the prior migraine preventive medication CRF.

For all other prior therapies that were being taken/used within 120 days prior to screening through the signing of the informed consent, therapy name, start and stop dates will be collected in the concomitant medication CRF.

### **7.8.2 Concomitant Treatment**

Throughout the study, investigators may prescribe any concomitant medications or treatments deemed necessary to provide adequate supportive care except for those listed in [Section 7.1.7](#).

Concomitant therapies are to be collected from signing of the informed consent through the end-of-study visit.

## **8. Discontinuation Criteria**

Subjects have the right to withdraw from IP and/or other protocol-required therapies, protocol procedures, or the study as a whole at any time and for any reason without prejudice to their future medical care by the physician or at the institution.

The investigator and/or sponsor can decide to withdraw subject(s) from IP, device, and/or other protocol-required therapies, protocol procedures, or the study as a whole at any time prior to study completion for the reasons listed in [Sections 8.1, 8.2.1, and 8.2.2](#).

### **8.1 Discontinuation of Study Treatment**

Subjects (or a legally acceptable representative) can decline to continue receiving IP and/or other protocol-required therapies or procedures at any time during the study but continue participation in the study. If this occurs, the investigator is to discuss with the subject the appropriate processes for discontinuation from IP or other protocol-required therapies and must discuss with the subject the possibilities for continuation of the Schedule of Activities (see [Section 2.2](#)) including different options of follow-up (eg, in person, by phone/mail, through family/friends, in correspondence/communication with other treating physicians, from the review of medical records) and collection of data, including endpoints, adverse events, and device-related events, as applicable and must document this decision in the subject's medical records/source documentation. Subjects who have discontinued IP and/or other protocol-required therapies or procedures should not be automatically removed from the study. Whenever safe and feasible, it is imperative that subjects remain on-study to ensure safety surveillance and/or collection of outcome data.

Subjects may be eligible for continued treatment with Amgen IP(s) and/or other protocol-required therapies by a separate protocol or as provided for by the local country's regulatory mechanism, based on parameters consistent with [Section 12.3](#).

Reasons for removal from protocol-required IP(s) or procedural assessments include any of the following:

- decision by sponsor
- lost to follow-up
- death
- ineligibility determined
- protocol deviation
- non-compliance
- adverse event
- subject request
- pregnancy

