### **8.2.2 Reasons for Removal From Study**

Reasons for removal of a subject from the study are:

- decision by sponsor
- withdrawal of consent from study
- death
- lost to follow-up

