#### **9.1.2 Treatment Period**

Study visits will occur per the Schedule of Activities ([Table 2-1](#)). The date of the first dose of IP is defined as day 1 and must occur 28 to 35 days from the Day -28 visit. On-study visits after Day 1 may be completed within  $\pm 3$  days. All subsequent doses and study visits will be scheduled based on the day 1 date. Administration of protocol-required therapies is to be administered once every 4 weeks during each visit that it is required.

Subjects who discontinue IP are encouraged to remain in the study and complete all remaining procedures and study visits.

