## 9. Statistical Methods of Analysis

### 9.1 General Considerations

All analyses will be conducted separately for subjects enrolled from traditional sites and subjects from DCTS. Formal statistical hypothesis testing for the primary and secondary endpoints will be performed for subjects enrolled from traditional sites only. Subject characteristics for both traditional sites and DCTS will be summarized descriptively.

Summary statistics by each treatment group will be tabulated at each assessment time point if applicable. For continuous endpoints, the descriptive statistics include: number of observations, means, medians, standard deviations, standard errors, first and third quartiles, minimums and maximums, and 2-sided 95% CIs of the means (CIs will be provided for efficacy endpoints only). For categorical endpoints, the summaries will contain the number and percentage of subjects in each category.

The primary analysis method utilizing a repeated measures linear mixed effects model will include all observed data regardless of treatment adherence.

A sequential testing procedure will be used to maintain the family-wise type 1 error  $\alpha = 0.05$  between the primary and secondary endpoints following the order of modified MIDAS total score, MMD, WPAI, MFIQ physical function, MFIQ usual activity, and MFIQ social function endpoints. An endpoint will only be tested if the endpoint tested in the previous step is statistically significant at 2-sided significance level of 0.05.

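### Protocol Sections 8 and 8.1 permit sites to stop outcome assessments for the same reasons as stopping IP, at odds with the protocol's own retention text and with estimands defined regardless of adherence

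*Protocol*

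**What the plan says.** - **Protocol Section 8** grants a discretionary power: "The investigator and/or sponsor can decide to withdraw subject(s) from IP, device, and/or other protocol-required therapies, protocol procedures, or the study as a whole". It may be used "at any time prior to study completion for the reasons listed in" Sections 8.1, 8.2.1 and 8.2.2.
- **Protocol 8.1** has a single list, introduced by "Reasons for removal from protocol-required IP(s) or procedural assessments include any of the following". The list includes ineligibility, protocol deviation, non-compliance, adverse event and pregnancy. It does not separate reasons to stop IP from reasons to stop assessments.
- **The same section** says that subjects who have stopped IP or procedures "should not be automatically removed from the study". It calls staying on-study imperative for safety surveillance or outcome data, where safe and feasible.
- **Protocol 8.2.2** ("Reasons for removal of a subject from the study are") gives four reasons only: sponsor decision, withdrawn consent, death and loss to follow-up.
- **Protocol 9.1.2** says "Subjects who discontinue IP are encouraged to remain in the study and complete all remaining procedures and study visits".
- **The estimands** (Protocol 4.1, SAP 2.1) name adherence as the intercurrent event and assess the effect regardless of it. The mixed model "will include all observed data regardless of treatment adherence" (SAP 9.1; Protocol 10.4.2.1 agrees).
- **Missing months** are left to that model under missing at random (MAR). Control-based multiple imputation is the sensitivity analysis (SAP 8.3, 9.5.1).

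**The concern.** Non-adherence is the only intercurrent event that the estimands name, and the chosen strategy is to keep measuring through it. That works only if outcomes are collected after IP is stopped or missed. A site that applies Section 8 and the 8.1 list as written may end the modified MIDAS, eDiary, WPAI and MFIQ of a non-compliant subject, and those are the months the strategy depends on.

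The MAR model would then estimate the missing months from subjects in the same arm who are still being assessed, most of whom are still on treatment. If the benefit fades after IP stops, the estimate moves from the effect regardless of adherence toward the effect had everyone adhered, in erenumab's favour. The five secondary endpoints average months 4 to 6, where most post-stop months fall, so they are exposed as well.

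**Working it through.** **1. The text, side by side**

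| Place | What it governs | Force |
|---|---|---|
| Section 8 | Withdrawal from IP, procedures or study, for reasons in 8.1, 8.2.1, 8.2.2 | Permissive |
| 8.1 list | IP or procedural assessments, one shared list | Reasons only |
| 8.1 retention paragraph | Staying on-study after stopping IP or procedures | Imperative, where safe and feasible |
| 8.2.2 | Removal from the study | Four reasons; no follow-up duty |
| 9.1.2 | Remaining visits after stopping IP | Encouraged |
| 7.6 | Consequence of repeated non-compliance | Study treatment only |
| Section 9 | Consequence of ineligibility found after enrolment | Study treatment only |
| 12.5 | Consequence of pregnancy | Study treatment only, citing 8.1 |

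The last three rows tie particular 8.1 reasons to treatment alone, so the reference to assessments in 8.1 is the outlier. No row withdraws the permission.

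**2. The plan's own figure**

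Inputs from Protocol Table 10-1: 120 per arm, difference −20, SD 43, two-sided alpha 0.05.

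- SE = 43 × √(2/120) = 5.55
- Power = Φ(20/5.55 − 1.96) = 95.0% (94.8% by noncentral t)

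The stated 94% reproduces to within rounding.

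**3. Size of the bias**

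Assumptions, none given in the documents:

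- A fraction p of each arm stops IP at random after month k = 1 to 5, each equally likely.
- The full monthly effect is 20/6 = 3.33. In erenumab stoppers it halves in the first month after stopping and is zero from then on.
- Every assessment after stopping is lost.

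Months of effect lost per stopper = 0.5 + (5 − k) = 5.5 − k, that is 4.5, 3.5, 2.5, 1.5 and 0.5. The mean is 2.5 months, or 2.5 × 3.33 = 8.33 points.

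With follow-up, the estimand value is −20 + 8.33p. With the post-stop months removed, MAR estimation averages −20, because those still observed carry the full effect. Under random stopping this does not depend on the covariance structure.

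| p | With follow-up | Overstatement | Share of estimand | In SEs (÷ 5.55) |
|---|---|---|---|---|
| 5% | −19.58 | 0.42 | 2.1% | 0.08 |
| 10% | −19.17 | 0.83 | 4.3% | 0.15 |
| 15% | −18.75 | 1.25 | 6.7% | 0.23 |

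A simulation under the same assumptions (1,500 trials per setting, visit correlation 0.4 or 0.6) gave 0.42, 0.83 to 0.85, and 1.27, with an SE of about 5.6.

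**4. Secondary endpoints (months 4 to 6)**

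The same pattern loses 3, 3, 2.5, 1.5 and 0.5 of the three months for k = 1 to 5. The mean is 10.5/5 = 2.1, or 70% of the effect per stopper. The overstatement as a share of the estimand is 0.70p/(1 − 0.70p): 3.6%, 7.5% and 11.7% for 5%, 10% and 15%.

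**5. Power**

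This illustration keeps the effect at −20. If 5%, 10%, 20% or 30% of each arm contribute nothing, power is 94.0%, 92.8%, 89.7% or 85.4%. If they are seen through month 1 only (AR(1), correlation 0.4 to 0.8), it is 94.2–94.5%, 93.3–94.0%, 91.0–92.8% or 87.8–91.0%. At loss of 5% to 10%, power moves little, and the main issue is what the estimate means.

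**The case against.** **8.1 and 8.2.2 are two tiers.** One covers treatment and procedures, the other the study, so different lists are to be expected. This stands. A reader might infer that 8.2.2 and 9.1.2 require follow-up while 8.1 forbids it, or that months are lost by rule. The documents support neither reading: 8.2.2 only limits removal from the study, 9.1.2 only encourages, and Section 8 only permits.

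**The retention paragraph already covers the case.** It does extend to subjects off procedures as well as off IP, and it is the strongest counterweight. But it asks that subjects stay on-study, which SAP 5.5 defines as randomized with no end-of-study visit yet. A subject taken off questionnaires still meets that definition. The duty to discuss continuing the Schedule of Activities arises when the subject declines, not when the investigator removes the subject.

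**Other sections tie these reasons to treatment only.** True of 7.6, Section 9 and 12.5, and good evidence of intent. It shows that the 8.1 phrase is out of line, but does not cancel it.

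**Procedural assessments is undefined.** Also true. Reading it to include the outcome instruments is an inference, though a natural one: Table 2-1 lists them in its procedure column under clinical outcome assessments.

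**Control-based imputation handles the bias.** In part. Imputing missing erenumab months from the placebo pattern comes close to the zero post-stop effect assumed above, and it is prespecified for the primary and all secondary endpoints. It remains a sensitivity analysis. The sequential tests use the MAR model, and imputation does not replace outcomes that could have been observed.

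**The size is a worst case.** This stands. Every IP stopper is assumed to lose every later assessment, whereas the wording affects only those whom a site chooses to take off assessments. End-of-study assessments for subjects who leave the study (Table 2-1 footnote, 9.1.3) would add a value, but 9.1.3 places that visit four weeks after the last dose, so it says little about later months.

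**Conclusion.** The inconsistency is real and worth correcting. Sections 8 and 8.1 together permit, without requiring, the loss of outcome months for reasons that include non-adherence, while the estimands and the analysis are defined regardless of adherence. The passages need to be reconciled.

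The consequence is modest. For the primary endpoint the overstatement is at most about 0.4 to 1.3 MIDAS points, up to about 0.2 SE. For the secondary endpoints it is larger in proportion. These figures rest on an assumed 5% to 15% stopping rate, an assumed fading of effect and complete loss of later visits. A reader might infer that the primary result would be seriously biased or the trial underpowered. The figures do not support that, and the planned control-based imputation gives a partial check.

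**What to change.** Reconcile Section 8, 8.1, 9.1.2 and the estimand text by separating two things that 8.1 now runs together:

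- **Reasons for stopping IP:** leave the list as it is.
- **Stopping outcome collection:** state that removal from IP for an 8.1 reason does not by itself end the modified MIDAS, eDiary, WPAI and MFIQ. These continue on schedule where safe and feasible, unless the subject asks to stop or an 8.2.2 reason applies.

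Keep the change to these four instruments. Tying withdrawal from every procedure to 8.2.2 would go too far: 8.2.2 has no adverse-event reason, so it would leave no such ground for stopping the wearable, for which 7.1.3 anticipates events such as allergic reaction. Other procedures and all treatment-stopping and safety provisions stay unchanged.

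The cost is a wording change by amendment or site memo. No visits or procedures are added, because these assessments are already scheduled. The downside is some extra follow-up effort for subjects off IP.

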## **8.2 Discontinuation From the Study**

Withdrawal of consent for a study means that the subject does not wish to receive further protocol-required therapies or procedures, and the subject does not wish to or is unable to continue further study participation. Subject data up to withdrawal of consent will be included in the analysis of the study, and where permitted, publicly available data can be included after withdrawal of consent. The investigator is to discuss with the subject appropriate procedures for withdrawal from the study and must document the subject's decision to withdraw in the subject's medical records/source documentation.

If a subject withdraws from the study, he/she may request destruction of any samples taken and not tested, and the investigator must notify Amgen accordingly (see [Section 12.6](#) for further details). Refer to the Schedule of Activities ([Table 2-1](#)) for data to be collected at the time of study discontinuation and follow-up and for any further evaluations that need to be completed.

### **8.2.1 Reasons for Removal From Washout, Run-in or Invasive Procedures**

Not applicable to this study.

### **8.2.2 Reasons for Removal From Study**

Reasons for removal of a subject from the study are:

- decision by sponsor
- withdrawal of consent from study
- death
- lost to follow-up

## **8.3 Lost to Follow-up**

A subject will be considered lost to follow-up if he or she repeatedly fails to attend scheduled visits and is unable to be contacted by the study site.

The following actions must be taken if a subject fails to attend a required study visit:

- The site must attempt to contact the subject and reschedule the missed visit as soon as possible and counsel the subject on the importance of maintaining the assigned visit schedule and ascertain whether or not the subject wishes to and/or is able to continue in the study.
- In cases in which the subject is deemed lost to follow-up, the investigator or designee must make every effort to regain contact with the subject (where possible, 3 telephone calls and, if necessary, a certified letter to the subject's last known mailing address or local equivalent methods). These contact attempts are to be documented in the subject's medical record/source documentation.

- If the subject continues to be unreachable, he/she will be considered to have withdrawn from the study with a primary reason of lost to follow-up.
- For subjects who are lost to follow-up, the investigator can search publicly available records (where permitted) to ascertain survival status. This ensures that the data set(s) produced as an outcome of the study is/are as comprehensive as possible.

## **9. Study Assessments and Procedures**

Study procedures and their time points are summarized in the Schedule of Activities (see [Table 2-1](#)).

As protocol waivers or exemptions are not allowed if an enrolled subject is subsequently determined to be ineligible for the study, this must be discussed with the sponsor immediately upon occurrence or awareness to determine if the subject is to continue or discontinue study treatment.

Adherence to the study design requirements, including those specified in the Schedule of Activities ([Table 2-1](#)), is essential and required for study conduct.

### **9.1 General Study Periods**

#### **9.1.1 Screening, Enrollment and/or Randomization**

##### **9.1.1.1 Screening Period**

Informed consent must be obtained before any screening procedure or discontinuation of standard therapy for any disallowed therapy. After the subject has signed the informed consent form, the site will register the subject in the IRT and screen the subject in order to assess eligibility for participation. The screening period is up to 7 weeks, which consists of an initial screening up to 3 weeks (21 days) and a 4-week (28 days) baseline. The screening period starts when ICF is signed and dated by the subject and ends when the subject completes baseline and is randomized or screen failed.

All screening evaluations must be completed and reviewed to confirm that potential subjects meet all eligibility criteria. The investigator will maintain a screening log to record details of all subjects screened and to confirm eligibility or record reasons for screening failure, (see [Section 6.6](#)) as applicable.

If a subject has not met all eligibility criteria at the end of initial screening or baseline, the subject will be registered as a screen fail. Screen fail subjects may be rescreened one time if the condition(s) leading to ineligibility are transient and expected to improve or resolve in a timely manner.

Rescreen subjects must first be registered as screen failures in IRT and subsequently registered as rescreens. Once the subject is registered as a rescreen, a new screening

period will begin. Subjects will retain the same subject identification number assigned at the original screening. If the rescreening period begins more than 60 days after the original signing of the informed consent form, all screening procedures, including informed consent, must be repeated.

#### **9.1.1.2 Baseline**

The 4-week (28 days) baseline starts when the subject has met all initial (Part 1) eligibility criteria (refer to [Section 6.1](#) and [Section 6.2](#)) and enters the baseline period. Baseline ends when the subject screen fails or does not meet all additional (Part 2) eligibility criteria (inclusion: [109](#) through [114](#); exclusion: [223](#) through [230](#)), or when subject meets all eligibility criteria and is enrolled and randomized.

#### **9.1.1.3 Randomization**

Upon completion of baseline, subjects found to meet eligibility requirements will undergo randomization and be assigned a study treatment.

#### **9.1.2 Treatment Period**

Study visits will occur per the Schedule of Activities ([Table 2-1](#)). The date of the first dose of IP is defined as day 1 and must occur 28 to 35 days from the Day -28 visit. On-study visits after Day 1 may be completed within  $\pm 3$  days. All subsequent doses and study visits will be scheduled based on the day 1 date. Administration of protocol-required therapies is to be administered once every 4 weeks during each visit that it is required.

Subjects who discontinue IP are encouraged to remain in the study and complete all remaining procedures and study visits.

#### **9.1.3 End-of-study**

The end-of-study visit occurs at week 24 or 4 weeks after last dose of IP for subjects who discontinue study. All assessments will be performed at the end-of-study visit as per Schedule of Activities ([Table 2-1](#)).

### **9.2 Description of General Study Assessments and Procedures**

The sections below provide a description of the individual study procedures for required time points.

#### **9.2.1 General Assessments**

##### **9.2.1.1 Informed Consent**

All subjects must sign and personally date the IRB/IEC approved informed consent before any study-specific procedures are performed.

Individuals recruited to the study as part of the DCTS will be provide electronic consent for their participation. A secure link to the web portal will be sent via email. Upon first access, the potential subject will receive a prompt to change the temporarily assigned password; the informed consent materials will then be presented through an electronic rendition of the IRB-approved consent document(s). Individuals will be able to review the consent document(s) and discuss the study with the investigator and/or designated study team member by telephone or videoconference, who will answer questions about the study and assess the individual's understanding.

Individuals who agree to take part in the study will provide their handwritten signature digitally executed to an electronic record using a computer mouse, touchscreen, or stylus on a computer or a tablet (depending on the capability of their web browser) in the designated signature block. The study team member administering the consent will countersign in the same manner. A copy of the fully executed consent documents will be provided to the subject, and the informed consent process will be documented and maintained as part of source documentation in the DCTS software.

